10.2.4 Surgical or Radiological Interventions to Stop Bleeding

The difference in proportion of subjects who undergo surgical or interventional radiological procedures to stop bleeding related to the primary injury up to 24 hours will also be analyzed using the Bayesian Logistic Regression and summarized in a similar manner to the primary endpoint.

Surgical or radiological interventions to stop bleeding will be identified as those procedures, that are entered into the eCRF as surgical procedures or interventional radiological procedures.

10.2.5 Supplemental Analysis for Secondary Endpoints

Secondary efficacy analyses as described above but based on the PP population will be conducted. For secondary endpoints the analysis will not be repeated for the ITT population.

10.2.6 Subgroup Analyses of Secondary Endpoints

The same subgroup analyses as for the primary endpoint will be conducted for secondary efficacy endpoints using the analyses described in [Section 10.1.4](#).

10.3 Analysis of Exploratory Endpoints

10.3.1 Transfusion of Blood Products

Transfusion of blood products is recorded according to the period in which the blood component transfusion started: before arrival at the hospital; from arrival at the hospital to time of randomization; from randomization to 6 hours after randomization; and from 6 to 24 hours after randomization. The assignment of blood products to specific periods will be based on the respective eCRF being used to enter the product.

The number of overall and by type of product in units per hour will be summarized for each treatment arm for each of the two post-randomization periods. Similarly, the summary will be repeated grouping the two periods into one up to 24 hours post-randomization period.

The hourly units will be determined by dividing the total units by the number of hours. For subjects who survived throughout the time span or who were discharged/discontinued, it will be assumed that the length of the time span matches the nominal length, e.g., from randomization to 6 hours after randomization, will be considered as 6 hours. For subjects who died in the time span and have known time of death, time of death – start of the time span will be used instead.

Hourly units will be compared between treatments using the Wilcoxon rank sum test, and the p-value will be displayed as an exploratory measure. Hodges-Lehmann estimates will be used to provide a 95% confidence interval for the median shift between treatments.

All transfusions will be listed.

10.3.2 **Death Due to Hemorrhagic Shock/Exsanguination**

Proportion of subjects with death due to hemorrhagic shock/exsanguination within 30 days of randomization will be analyzed in the same manner as the primary endpoint. Subjects who died due to other causes will be included in the analysis and not considered events.

All deaths, including primary cause, date and time, time from randomization till death, and cause of death will be listed.

10.3.3 **Ventilator-free Days, ICU-free Days and Hospital-free Days**

A summary table will be shown summarizing each of the following using the mITT Population:

- Number of days on ventilator during primary hospital stay up to 30 days after randomization.
- Number of days in ICU during primary hospital stay up to 30 days after randomization.
- Primary hospital length of stay (days) up to 30 days after randomization.

Additionally, the following parameters will be both summarized and inferential statistics will be provided for them:

- Number of ventilator-free days .
- Number of ICU-free days.
- Number of hospital-free days.

Hospital length of stay will be calculated directly as date of discharge/death/discontinuation – date of randomization + 1 day, as in this study time in the study is the same as time in the (primary) hospital. Hospital lengths stay larger than 30 days should not occur, but if they do, hospital length of stay will be set to 30 days instead.

Missing start and end dates for ventilation and ICU will be replaced with the start and end date of the in-hospital period respectively. End dates that are after the end date of the in-hospital period will also be replaced with the end date of the in-hospital period for this calculation.

As subjects should be followed up for 30 days, any end date later than study day 30 will be replaced with the date of study day 30. Episodes that start after study day 30 will be disregarded entirely.

If multiple episodes are recorded for ventilation or ICU stay, the duration for each episode will be calculated and summed up, except that for cases where the end date of one episode coincides with the start date of the next, in which case the episodes are combined before calculating the duration in order to avoid counting the same day twice.

The number of ICU-free days, ventilator-free days and hospital-free days is calculated as 30 days less the number of days in ICU, on ventilator and in hospital respectively for subjects who do not die and who did not withdraw from the study or decline to continue participation. For subjects who die, it will be set to zero instead.

Subjects who withdrew or declined to continue participation will not be included in the main analysis, but a supplemental worst-case analysis will be conducted. For this worst case analysis the number of free days for subjects who withdrew or declined to continue participation will be calculated as study duration – number of days in ICU/on ventilation/in hospital respectively. The number of free days for all other subjects will be the same as in the main analysis.

The summaries will include statistics such as mean, median, standard deviation, minimum, maximum and the 25% and 75% quantiles. Confidence intervals for the mean based on the t-distribution and non-parametric confidence intervals for the medians based on Hodges-Lehmann estimates will be presented. A Wilcoxon rank-sum test will be conducted between the placebo and the active group, and the p-value will be presented as an exploratory analysis.

These variables will also be listed, including details on start and end dates of the episodes.

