2.3.2 Exploratory Endpoints

The exploratory endpoints (and corresponding summary measures) of the study are as follows:

Exploratory Objective	Endpoint	Summary Measure
1	Transfusion of blood products	Number of units of blood products transfused before arrival at the hospital through the first 24 hours after randomization, overall and by type of product by treatment
2	Ventilator-free days	Number of ventilator-free days during the primary hospital stay up to 30 days after randomization, by treatment
2	ICU-free days	Number of ICU-free days during the primary hospital stay up to 30 days after randomization, by treatment
2	Hospital length of stay	Number of days of primary hospitalization

Details regarding how the exploratory endpoints will be calculated and adjusted for deaths will be provided in the statistical analysis plan (SAP).

3 Study Design and Oversight

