4	Serious adverse events (SAEs) considered related to IP	During the primary hospital stay only, within the 30 days after randomization: 
 • Number and proportion of subjects with SAEs considered related to IP by treatment (BE1116 or placebo)

Objectives	Endpoints	Summary Measure(s)
4	
Adverse events of special interest (AESIs):
 
 • Thromboembolic events (TEEs), symptomatic or asymptomatic, and arterial or venous (eg, deep vein thrombosis, pulmonary embolism, ischemic stroke [including thromboembolic stroke], myocardial infarction) • Acute respiratory distress syndrome (ARDS) • Multiple organ failure • Acute kidney injury (AKI) requiring renal replacement therapy (dialysis, hemofiltration, or hemodiafiltration) 
Note: superficial thromboses will not be included as AESI
	
 • TEEs: Number and proportion of in-hospital overall and related TEEs up to 30 days after randomization by treatment (BE1116 or placebo) • Number and proportion of subjects with the following: 
 ○ ARDS ○ Multiple organ failure ○ AKI requiring renal replacement therapy
Exploratory		
1	Transfusion of blood products	Number of units of blood product transfused before arrival at the hospital through the first 24 hours after randomization, overall and by type of product by treatment
2	Ventilator-free days	Number of ventilator-free days during the primary hospital stay up to 30 days after randomization, by treatment
2	Intensive care unit (ICU)-free days	Number of ICU-free days during the primary hospital stay up to 30 days after randomization, by treatment
2	Hospital-free days	Number of hospital-free days up to 30 days after randomization, by treatment

Objectives	Endpoints	Summary Measure(s)
3#	Infusion of tranexamic acid	Amount of tranexamic acid infused in milligram (mg) before arrival at the hospital through the first 24 hours after randomization, overall and by treatment
4#	Death due to hemorrhagic shock/exsanguination	Difference in proportion of deaths that are due to hemorrhagic shock/exsanguination in-hospital in the BE1116 arm compared with the placebo arm up to 30 days after randomization, as estimated by a Bayesian logistic regression model

*In-hospital mortality will only be recorded and assessed for the primary hospitalization.

#Additional endpoints not defined in the CSP but added in the SAP.

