10.3.4 Tranexamic Acid

The amount of infused tranexamic acid measured in mg will be summarized descriptively in the same way as the blood products described in [Section 10.3.1](#).

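### SAP 10.3.1 and 10.3.4 analyse blood products and tranexamic acid after randomization only, blood products only per hour, so the totals defined in Table 1 are never tabulated and the mean hourly rate partly reflects early mortality

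*SAP*

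**What the plan says.** **Defined endpoints.** Protocol 2.3.2 gives the transfusion endpoint as "Number of units of blood products transfused before arrival at the hospital through the first 24 hours after randomization", overall and by type of product, and SAP Table 1 (section 4.1) repeats it. Table 1 adds a tranexamic acid endpoint that the protocol does not have: "Amount of tranexamic acid infused in milligram (mg) before arrival at the hospital through the first 24 hours after randomization, overall and by treatment". Both are totals, and both windows open before hospital arrival.

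**Planned analysis of blood products.** SAP 10.3.1 names four recording periods, two before and two after randomization. It then says amounts "in units per hour will be summarized for each treatment arm for each of the two post-randomization periods", and repeats this for the combined 0–24 hours. "The hourly units will be determined by dividing the total units by the number of hours". Survivors and subjects discharged or discontinued get the nominal length (6, 18 or 24 hours). For subjects who die in the period at a known time, "time of death – start of the time span will be used instead". Arms are compared on the hourly values by Wilcoxon rank sum test with a Hodges-Lehmann interval. Individual transfusions are listed, but no table of total units is specified.

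**Planned analysis of tranexamic acid.** SAP 10.3.4 says the amount, in mg, "will be summarized descriptively in the same way as the blood products described in" 10.3.1.

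**Elsewhere.** SAP 9.3 puts pre-randomization transfusions, and whether tranexamic acid was given before study product, in the baseline summary. SAP 10.1.4 has a yes/no subgroup for prior tranexamic acid. Neither mentions a pre-randomization amount of tranexamic acid. SAP 5.2 declares tranexamic acid as an added endpoint. Nothing in section 5 declares the move from totals to post-randomization hourly values.

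**The concern.** There are two separate problems.

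The first is that the reported quantity is not the defined one. A reader of the study report who looks for the Table 1 endpoints will find a different scale over a shorter window, with no stated reason. A subject given 2 g of tranexamic acid before or on arrival and none later has 2000 mg under Table 1 and nothing in the post-randomization periods.

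The second is that the divisor depends on survival. Bleeding patients are usually transfused most heavily at the start. A subject who dies early is divided by a short time that covers only this heavy phase. A survivor is divided by 24 hours, most of it with little transfusion. The arm with fewer early deaths can then show a lower mean hourly use although nobody's need has changed. Protocol 1.4 names decreased transfusion as a potential benefit, so this mean could be read as support for it.

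**Working it through.** The documents give no figure for this endpoint, so there is none to reproduce. The mortality rates come from the plan; the transfusion patterns are assumptions.

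**Step 1. Definition against analysis.**

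| | Defined | Analysed |
|---|---|---|
| Blood products, scale | units | units per hour |
| Blood products, window | before arrival to 24 h | 0–6 h, 6–24 h, 0–24 h after randomization |
| Tranexamic acid, scale | mg | mg, handled as in 10.3.1 (possibly per hour) |
| Tranexamic acid, window | before arrival to 24 h | as in 10.3.1, so post-randomization |

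**Step 2. One subject.** Take 10 units, all given in the first hour.
- Death at 1 h: 10/1 = 10 units/h.
- Survivor, 0–6 h: 10/6 = 1.67 units/h, a ratio of 10/1.67 = 6.
- Survivor, 0–24 h: 10/24 = 0.42 units/h, a ratio of 24/1 = 24.

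**Step 3. The arm mean when treatment affects mortality only.** Let p be the 6-hour death rate in an arm, and let k be the mean hourly rate in early deaths divided by that in the others, with both group means equal across arms. Then

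ratio of mean rates (BE1116/placebo) = [1 + p_B(k − 1)] / [1 + p_P(k − 1)].

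Use p_P = 0.10 and p_B = 0.08. The 10% placebo rate is in SAP 16.2.5, and 8% is the 20% relative reduction in Table 4. As a check that this is the right reading of that row, a normal-approximation simulation of the original sequential design gave 83.4% power (Table 4: 82.9%) and 1.93% type I error (Table 4: 1.94%).

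To obtain k, two arms of 200,000 subjects were simulated with an identical transfusion process. The assumptions were about 6 units in the first 6 h; exponential decay with constant 2 or 4 h; median time of early deaths 1.5 or 3 h; and fatal bleeders transfused at 1 or 2 times the rate of the others. Three of the eight combinations, for 0–24 h:

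| Fatal-bleeder multiple, decay, median death | Rate in deaths | Rate in others | k | Ratio by formula | Ratio simulated |
|---|---|---|---|---|---|
| 1×, 4 h, 3 h | 1.407 | 0.322 | 4.4 | 1.27/1.34 = 0.95 | 0.947 |
| 1×, 2 h, 1.5 h | 2.190 | 0.263 | 8.3 | 1.586/1.733 = 0.915 | 0.915 |
| 2×, 2 h, 1.5 h | 4.410 | 0.263 | 16.8 | 2.26/2.58 = 0.88 | 0.877 |

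Over all eight combinations the simulated ratio was 0.88–0.95 for 0–24 h (a 5–12% drop) and 0.95–0.99 for 0–6 h (a 1–5% drop). Two further simulations with other assumed inputs gave drops of 6–11% and 6–13% for 0–24 h. Total post-randomization units in the eight combinations had ratios of 0.99–1.01.

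Two limits follow from the formula. With a constant transfusion rate in everyone, k = 1 and the drop vanishes. As k grows, the ratio tends to p_B/p_P = 0.80, so under these assumptions the drop cannot exceed 20%.

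**Step 4. The planned test.** Suppose every early death outranks every other subject and the rest are exchangeable. The probability that a random placebo subject outranks a random BE1116 subject is 0.5 + (p_P − p_B)/2 = 0.5 + 0.02/2 = 0.51. For placebo rates of 8% and 12% with the same relative reduction it is 0.508 and 0.512.

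A simulation with 700 per arm and 400 trials (assumed gamma-distributed need with mean 8 units, a 1.5 h time constant, and death risk proportional to need) gave these results at 10% v 8%:
- median hourly use: 0.250 v 0.248;
- Wilcoxon rejection rate: about 7% on hourly units and 5% on totals, against 6.5% and 5.5% with no mortality difference.

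The simulation standard error near 5% is √(0.05 × 0.95/400) ≈ 1.1 points.

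**The case against.** The strongest reply is that the rate is deliberate and allowed. Protocol 2.3.2 leaves it to the SAP to say how exploratory endpoints are calculated and adjusted for deaths, and dividing by time at risk is such an adjustment. Totals are not neutral either, because death cuts them short: in a simulation at 10% v 7% with no effect on need, mean totals were 7.4 v 7.6 units, slightly higher in the better-surviving arm. This stands, and it is why totals should be added rather than substituted. It does not explain why the total is never tabulated, or why the change goes undeclared.

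Leaving pre-randomization units out of the treatment comparison is also defensible for blood products. Treatment cannot affect them, and 9.3 already summarizes prior transfusion.

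Three stronger readings are tempting, and the documents do not support them.
- A reader might infer that the planned comparison mostly re-counts early deaths. The distortion is in the mean. The comparison in 10.3.1 is rank-based, SAP section 7 also reports medians and quartiles, and Step 4 shows that these hardly move.
- A reader might take tranexamic acid to be analysed in mg per hour. Section 10.3.4 says mg and refers to 10.3.1 for the method, so the hourly reading is possible but not certain.
- A reader might conclude that tranexamic acid exposure cannot be compared between arms at all. Use before study product is tabulated and is a subgroup factor. What is missing is the pre-randomization amount.

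**Conclusion.** The mismatch holds on the text. The defined totals, and any pre-randomization tranexamic acid amount, appear in no table that the SAP specifies, and section 5 is silent about it.

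The survival-dependent divisor has a modest effect. At 10% v 8% the mean 0–24 h rate is about 5–13% lower in the better-surviving arm with no effect on need. That range rests on assumed front-loaded transfusion, and the documents give no data on the pattern. It would be larger with a larger mortality difference and nil with a constant transfusion rate. The direction is not in favour of BE1116 as such: it favours whichever arm has fewer early deaths.

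Both endpoints are exploratory, their p-values are unadjusted, tranexamic acid is descriptive only, and no success criterion depends on either. This is a low-priority correction to reporting and interpretation.

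**What to change.** - **SAP 10.3.1.** Keep units per hour and the Wilcoxon test. Add total units by arm for 0–6 h, 0–24 h and the Table 1 window, overall and by product, for all subjects. State that the mean hourly rate is to be read only alongside the totals and mortality. If totals are also split by alive or died, label the split descriptive, because it conditions on an outcome that treatment may change.
- **SAP 10.3.4.** Report the number of subjects given tranexamic acid and the total mg by arm from pre-hospital through 24 h, split before and after randomization, and not divided by hours.
- **SAP section 5.** Declare the hourly scale and the post-randomization window as a change from the protocol's definition, with the reason.

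The cost is a few extra table rows. The units by period are already recorded, and Table 1 already presumes that the mg are. The remaining weakness is that totals are truncated by death, which is why the rate stays beside them. No primary or secondary analysis changes.

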8.2.2 Durations

Durations (eg, the duration of an adverse event [AE]) are calculated in days, hours, and minutes as:

- event end date – event start date + 1 day if end time or start time not available.
- event end date / time – event start date / time if both end time and start time available.

Thus, there will be no duration of 0 if end time or start time are not available. If an AE has missing or partially missing start or end date, no duration will be calculated. If duration is provided in a listing, then start and end date will also be included.

For cases, where multiple durations are added up for time on ventilator or time in the ICU see the specific rules provided in [Section 10.3.3](#).

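### SAP 10.3.3 fills missing ventilator and ICU dates in a way that can make episodes overlap, but merges only episodes that touch, so shared days are counted twice

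*SAP*

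**What the plan says.** SAP 10.3.3 derives ventilator, ICU and hospital days and the matching free days in these steps.

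- Missing dates: "Missing start and end dates for ventilation and ICU will be replaced with the start and end date of the in-hospital period respectively". No exception is made for a subject with several episodes.
- Late dates: an end date after the in-hospital period is pulled back to its end, and "any end date later than study day 30 will be replaced with the date of study day 30".
- Several episodes: "the duration for each episode will be calculated and summed up". The one exception is where "the end date of one episode coincides with the start date of the next"; those episodes are joined first, "in order to avoid counting the same day twice".
- Free days in the main analysis: the number "is calculated as 30 days less the number of days in ICU, on ventilator and in hospital respectively for subjects who do not die" and did not withdraw or decline further participation. Deaths get zero.
- Free days in the supplemental worst-case analysis: for subjects who withdrew or declined, study duration minus the days used.

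The 30-day ceiling is written for hospital length of stay only. Ventilator and ICU days have no ceiling, and free days have no floor. SAP 8.2.2 (Durations) gives a general duration rule but refers to 10.3.3 for summed ventilator and ICU durations, so no other section deals with overlap.

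**The concern.** The fill rule produces a pattern that the merge rule does not cover. A missing end on an earlier episode is moved to the end of the hospital period, past the start of the next episode. A missing start on a later episode is moved to the start of the hospital period, ahead of the previous episode's end. In both cases the episodes overlap instead of meeting on one date, so the exception does not apply and the shared days enter the sum twice.

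ICU or ventilator days could then exceed the hospital stay in the summary tables, and free days would be understated, sometimes below zero. These values feed the means with t-based intervals, the Hodges-Lehmann intervals and the Wilcoxon rank-sum tests in 10.3.3. Because deaths are scored zero, a survivor with a negative value would be ranked as worse than death.

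**Working it through.** The plan gives no figure to reproduce, so the check applies the written rule to example episodes. The episode dates are assumptions chosen for illustration; the documents contain no subject data.

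**Rule as written (SAP 10.3.3).** Fill missing dates, cap the ends at the in-hospital end and at Day 30, join episodes only if one end date equals the next start date, then:

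- episode days = end − start + 1
- days = sum over episodes
- free days = 30 − days

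**Comparison.** Use the same filled and capped dates, but count each calendar day once.

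| Episodes as recorded | Stay | Days by the rule | Free | Each day once | Free |
|---|---|---|---|---|---|
| Days 1-8; Days 15-20 | 30 | 8 + 6 = 14 | 16 | 14 | 16 |
| Days 1-8; Days 8-20 | 30 | joined, 20 | 10 | 20 | 10 |
| Days 1-5; no start, ends Day 12 | 12 or more | 5 + 12 = 17 | 13 | 12 | 18 |
| Day 1, no end; Days 12-15 | 20 | 20 + 4 = 24 | 6 | 20 | 10 |
| Day 1, no end; Days 8-20 | 20 | 20 + 13 = 33 | −3 | 20 | 10 |
| Days 1-8; no start, ends Day 25 | 30 | 8 + 25 = 33 | −3 | 25 | 5 |
| Day 1, no end; Days 15-20 | 30 | 30 + 6 = 36 | −6 | 30 | 0 |
| Day 1, no end; Day 10, no end | 25 | 25 + 16 = 41 | −11 | 25 | 5 |

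The first two rows are controls: for separate episodes and for touching ones the written rule is correct. The error appears only where the fill creates an overlap.

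**When the main analysis goes negative.** Take two episodes in a stay of L days, the first from Day 1 with no end and the second from Day 2 to Day L. The sum is L + (L − 1). At L = 15 it is 29, leaving 1 free day. At L = 16 it is 31, leaving −1. So 16 days is the shortest stay at which two episodes can produce a negative value. In shorter stays the value is too low but not negative.

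**Worst-case analysis.** Study duration 10 days, Day 1 with no end plus Days 5-10: 10 + 6 = 16 days, and 10 − 16 = −6. Here the subtraction starts from study duration, so a short stay is enough.

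**A single episode.** Day 1 with no end in a 30-day stay gives 30 days and 0 free days. Double counting therefore needs at least two episodes of the same type.

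**The case against.** The strongest reply is that this needs an uncommon combination: two or more ventilator or ICU episodes in one subject, and a missing date in a particular place. A missing end on the last episode, or a missing start on the first, creates no overlap. Protocol 13.5.2 provides electronic consistency checks with queries to be resolved, and an open-ended episode followed by a later one is an obvious query. The episode dates are also listed, so an impossible total would be visible. The SAP states its purpose, so a programmer might merge overlaps anyway. The endpoints are exploratory, and the same rule applies in both arms. All of this stands and limits the weight of the point. It does not change what the rule yields if it is programmed as written.

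A reader might infer two stronger things that the documents do not support.

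- *That ventilator, ICU and hospital days are on different scales.* SAP 8.2.2 uses elapsed time when both times are known and "event end date – event start date + 1 day if end time or start time not available", and Protocol 8.1.4.1 collects times for ventilator and ICU use but only dates for hospitalization. On that reading, Day 1 14:00 to Day 3 10:00 is 44 hours, or 1.83 days, against 3 calendar days. But 8.2.2 refers to 10.3.3 for summed durations, and 10.3.3 is worded in dates. Joining episodes that share a date prevents double counting only if both end dates are counted in full. Calendar days are the natural reading. What remains is an ambiguity: the reference to 10.3.3 speaks of multiple durations, so a single episode could still be read under 8.2.2.
- *That negative values are typical, or that the treatment comparison is biased in one direction.* Negative values in the main analysis need summed days above 30, and nothing in the documents shows that missing dates would fall unequally between arms.

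**Conclusion.** The point holds as a defect in the written rule. Followed literally, SAP 10.3.3 counts days twice whenever the fill makes two episodes overlap. In the examples the excess runs from 4 days (24 against 20) to 16 days (41 against 25). Free days are then too low, and in the main analysis they are negative once the sum exceeds 30, which places a survivor below subjects who died.

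The examples rest on assumed episode dates and on counting inclusive calendar days. How many subjects would have the required pattern is not known from the documents. Only exploratory endpoints and their descriptive summaries are touched; the primary analysis and the gated secondary tests are unaffected. The matter is minor, but the rule can return impossible values and is easily corrected.

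**What to change.** Replace the merge sentence in SAP 10.3.3 with a rule to this effect: after imputation and truncation, all ventilator episodes, and separately all ICU episodes, that overlap or touch are combined, and each calendar day within study Days 1-30 is counted once. ICU and ventilator days then cannot exceed the hospital length of stay, and free days cannot fall below zero in either the main or the worst-case analysis.

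In the same sentence, confirm that single and multiple episodes are both counted in inclusive calendar days, as hospital stay is, and not as elapsed time under 8.2.2.

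The rule for filling missing dates can stay as it is. Limiting an imputed date by the neighbouring episode would be a separate choice and is not needed to remove the double count.

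The cost is rewording a few sentences and programming a day-by-day flag. No new data are needed, and it can be settled before database lock.
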